1.3 Evaluation method

Before and after treatment, a dedicated person is assigned to assess whether the patient is in the control group or treatment group, which is a third-party blind assessment. Evaluate lower limb motor function using the Fugl Meyer method (total lower limb motor score 34 points, total balance score 14 points). Muscle strength, muscle tone examination, motor function, and self-care ability scores. And record the peak torque (PT) at an angular velocity of $60^{\circ}/s$. The reason for choosing this angle is because most of our subjects find it difficult to produce faster movements. PT refers to the maximum torque output generated by muscle contraction, representing the maximum muscle force generated by muscle contraction, in $N \cdot m$. In isokinetic muscle strength testing, the PT value has high accuracy and repeatability, and is considered the golden indicator of isokinetic muscle strength testing. It has high repeatability, and the peak torque measurement of knee joint flexion and extension is particularly stable. At the same time, a satisfaction questionnaire survey

was conducted on the use of different isokinetic methods, quantifying the characteristics of the two types of isokinetic methods based on the results: the survey content includes patients' comfort, satisfaction, and treatment effectiveness; Therapist: Conduct statistics on operability, learning curve, economy, and other aspects.

2 Statistical analysis

SPSS 23.0 software was used for data statistical analysis. The measurement data is represented by the mean \pm standard deviation, the inter group comparison is performed using one-way analysis of variance, the pairwise comparison between groups is performed using LSD test, the mean comparison between two samples is performed using t-test, and the rate comparison of categorical data is performed using chi square test. $P < 0.05$ indicates a statistically significant difference.

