1.1 General information

A total of 90 stroke hemiplegic rehabilitation patients who were hospitalized in the Rehabilitation Department of Qianfoshan Hospital in Shandong Province from January 2022 to January 2023 were selected, meeting the diagnostic criteria for cerebral infarction and cerebral hemorrhage in the 2007 edition of the Chinese Guidelines for the Prevention and Treatment of Cerebrovascular Diseases, and confirmed by cranial CT or MR examination; All of them are first-time onset, with a course of \leq 1 month, and the lower limb of the hemiplegic side is classified as stage III or above. All participants signed an informed consent form. All patients have stable vital signs, stable condition, cooperative examination, no severe cognitive, visual, hearing impairment, no sensory aphasia, no orthopedic diseases, no lower limb muscle pain, no history of congenital diseases or other brain diseases, no history of organic or functional mental illness. Divide patients into a control group and a treatment group using a random number table method. There are 30 cases in the control group, 30 cases in the intelligent isokinetic treatment group, and 30 cases in the traditional isokinetic treatment group.

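### The between-group ANOVA names no response variable and makes no use of baseline, although outcomes are assessed before treatment

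*Combined protocol and SAP*

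**What the plan says.** Section 1.3 (Evaluation method) sets the timing: "Before and after treatment, a dedicated person is assigned" to carry out a blinded assessment. It then lists the Fugl-Meyer scores ("total lower limb motor score 34 points, total balance score 14 points"), muscle strength, muscle tone, motor function, self-care and peak torque at 60°/s. None is named as primary.

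Section 2 (Statistical analysis) is the whole analysis plan. For continuous data, "the inter group comparison is performed using one-way analysis of variance, the pairwise comparison between groups is performed using LSD test", and "the mean comparison between two samples is performed using t-test". The significance threshold is P < 0.05. The section does not name the variable that enters the ANOVA. No section mentions a change score, a baseline covariate, a repeated-measures model or a group-by-time term.

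Section 1.1 (General information) gives 90 patients, 30 in each of three groups, and says of allocation: "Divide patients into a control group and a treatment group using a random number table method".

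**The concern.** Two different analyses fit the text. One compares post-treatment values; the other compares changes from baseline. They have different power, and a chance baseline difference between arms pushes them in opposite directions. A plan that leaves both open lets the response be chosen once results are known.

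Neither analysis makes the best use of the baseline. Post-treatment values leave baseline spread in the error term. Change scores fix the baseline slope at 1 instead of estimating it. With 30 per arm, precision is limited to begin with, and the baseline is already collected.

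**Working it through.** **Inputs from the documents.** 30 per arm (Section 1.1; 3 × 30 = 90 agrees with the stated total) and P < 0.05 (Section 2). The documents give no power, effect size, SD or correlation, so there is no figure of the plan's own to reproduce.

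**Assumptions.** Two-sided test; true difference 0.5 of the post-treatment SD; pairwise LSD tests read without requiring a significant overall F test; pre-post correlation r from 0.3 to 0.8; k = SD before / SD after = 1, varied below.

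**Formulas.** With the post-treatment SD set to 1, the effective SD is:
- post-treatment value: 1
- change: √(1 + k² − 2rk)
- ANCOVA: √(1 − r²) × √(1 + 1/85), where the second factor allows for estimating the slope

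The standard error of a pairwise difference is SD × √(2/30) = SD × 0.258. Power comes from the noncentral t with noncentrality 0.5 / SE, on 87 df for ANOVA and 86 df for ANCOVA.

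*Example, r = 0.7, k = 1.* The change SD is √0.6 = 0.775, the noncentrality is 0.5 / (0.775 × 0.258) = 2.50, and power is 69.6%. The ANCOVA SD is √0.51 × √(86/85) = 0.718, the noncentrality is 2.70, and power is 76.0%.

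**Power per pair**

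| r | Post-treatment | Change, k = 0.7 | Change, k = 1 | Change, k = 1.3 | ANCOVA, any k |
|---|---|---|---|---|---|
| 0.3 | 48.2% | 45.7% | 36.7% | 28.3% | 51.4% |
| 0.5 | 48.2% | 57.7% | 48.2% | 36.9% | 59.4% |
| 0.7 | 48.2% | 76.5% | 69.6% | 53.7% | 76.0% |
| 0.8 | 48.2% | 88.3% | 85.7% | 68.9% | 88.7% |

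At r = 0, ANCOVA has 47.8% against 48.2% for post-treatment values.

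Change scores beat post-treatment values only when 1 + k² − 2rk < 1, that is, when r > k/2: 0.35 at k = 0.7, 0.5 at k = 1 and 0.65 at k = 1.3. Which of the two open analyses is stronger therefore depends on quantities the documents do not give.

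**Expected 95% CI half-width (k = 1, in SDs, r = 0.3, 0.5, 0.7, 0.8).** Post-treatment: 0.51 throughout. Change: 0.61, 0.51, 0.40, 0.32. ANCOVA: 0.49, 0.45, 0.37, 0.31.

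**If LSD is gated by the overall F test.** I took the third arm's mean at or between the means of the pair (simulation, 40,000 trials per setting, k = 1). Post-treatment power falls to 35–40%. ANCOVA gives 38–43%, 47–52%, 65–71% and 81–86% at the four values of r. The ordering does not change.

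**Chance imbalance.** The standard error of a baseline difference between two arms is 0.26 SD. At r = 0.7 and k = 1, an imbalance of that size shifts the post-treatment contrast by 0.7 × 0.258 = +0.18 SD and the change contrast by (0.7 − 1) × 0.258 = −0.08 SD.

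**The open choice.** I simulated three-arm trials under the null (equal SDs, one ungated pair). Each analysis alone rejects in about 5%. Rejecting when either is significant gives about 9% at every r from 0.3 to 0.8.

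**The case against.** The strongest reply separates the two parts. The unnamed response is a real gap, but unadjusted ANOVA after randomisation is a valid test, so adding a covariate is an efficiency gain and not the repair of an error. That is right, and no bias is claimed for either analysis fixed in advance. The two parts still belong together, because one step closes the choice and recovers the precision.

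The size of the gain also rests on assumptions. Over post-treatment values it runs from −0.4 points (r = 0) to about 41 points (r = 0.8), and it is only about 1 point at r = 0.2. Over change scores, within the tabulated cases, it runs from −0.5 points (k = 0.7, r = 0.7) to 23 points (k = 1.3, r = 0.3). This stands as a limit on magnitude. It does not weaken the recommendation, since the worst loss found is about half a point.

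Three narrower objections hold as conditions:
- Section 1.1 describes a split into control and treatment and then lists three groups. Validity of the intelligent-versus-traditional comparison assumes that the random number table allocated all three.
- The peak torque sentence carries no timing of its own. That it is also measured before treatment is a reasonable reading, not an explicit statement.
- Patients "from January 2022 to January 2023 were selected", in the past tense. If outcomes have been seen, the precision gain cannot be claimed for a pre-specified analysis.

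**Conclusion.** The concern holds. The plan does not identify the response in its main between-group test and does not adjust for a baseline that it collects. This should be corrected, though it does not invalidate the trial.

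Under the stated assumptions, ANCOVA adds about 3, 11, 28 and 41 power points over post-treatment values at r = 0.3, 0.5, 0.7 and 0.8. With equal SDs it adds about 15, 11, 6 and 3 points over change scores. Leaving the response open allows the error rate for a single pair to reach about 9% instead of 5%. Nothing in the documents shows that the choice was made after seeing results; the plan simply does not rule it out. The gap itself is certain from the text. Its size depends on the unknown correlation and SD ratio and on the assumed 0.5 SD difference.

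**What to change.** - For each outcome treated as continuous (Fugl-Meyer lower limb and balance, self-care score, peak torque at 60°/s), name the post-treatment value as the response. Fit ANCOVA with group (three levels) and the baseline value of the same outcome. Report adjusted pairwise differences with 95% CIs.
- Confirm that peak torque is measured before treatment. Check residuals for the bounded scores, balance in particular with its ceiling of 14. If strength or tone is graded ordinally, use a baseline-adjusted ordinal model.
- State whether the pairwise LSD tests are read only after a significant overall test.
- As a separate wording gap, say what the two-sample t-test is for. It may be an independent test for the questionnaire aimed at "quantifying the characteristics of the two types of isokinetic methods", or a paired within-group test of before against after. The latter should be descriptive only.
- If outcome data have already been seen, label the ANCOVA post hoc and report the planned ANOVA beside it, stating which response it used.

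The cost is one degree of freedom (86 instead of 87) and, in the cases computed, at most about half a power point. No new data are needed.

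### Does the plan need a test for ordered data because muscle strength, muscle tone and the questionnaire items have no named scale and no assigned test?

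*Combined protocol and SAP*

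**What the plan says.** Section 1.3 gives the Fugl-Meyer score with its maxima (34 for lower-limb motor function, 14 for balance) and peak torque with a unit and a test speed. It then lists, with no scale, "Muscle strength, muscle tone examination, motor function, and self-care ability scores". Of the patient questionnaire it says that "the survey content includes patients' comfort, satisfaction, and treatment effectiveness", again with no response format. The stated aim of the survey is "quantifying the characteristics of the two types of isokinetic methods based on the results", so that comparison has two groups, not three.

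Section 2 assigns methods by data type. Measurement data are summarised by mean and standard deviation; "the inter group comparison is performed using one-way analysis of variance, the pairwise comparison between groups is performed using LSD test", and two samples are compared by t-test. For categorical data, "the rate comparison of categorical data is performed using chi square test". No outcome is named in Section 2, and no rank-based, trend or ordinal-model method is listed.

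On group sizes, Section 1.1 says "There are 30 cases in the control group, 30 cases in the intelligent isokinetic treatment group", with a further 30 on traditional isokinetic treatment: 3 × 30 = 90, which agrees with the stated total.

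**The concern.** Muscle strength, muscle tone and satisfaction are often recorded as a few ordered grades. That is an assumption here, since the scales are not named. Peak torque is recorded separately, so it does not supply the scale for muscle strength. If the items are graded, neither listed route was designed for them. Chi-square on the full table of grades ignores their order, and chi-square on a collapsed rate throws part of it away. With only 30 patients per arm, the power lost could be worth having. A route left open also leaves room to choose the test once the data have been seen.

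**Working it through.** The plan states no power, effect size or standard deviation, so there is no figure of its own to reproduce. The question is how much the open choice of test matters.

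**Inputs.** From the documents: 30 per arm (Section 1.1), a 0.05 threshold and the listed tests (Section 2). Assumed: two-sided testing, the number of grades, the control distribution, and a proportional-odds shift with odds ratio (OR) 2, 3 or 4.

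**Shift.** If C is the control group's cumulative proportion at a cut, the treated group's cumulative odds are [C/(1 − C)]/OR. Take five grades with control proportions 10/20/40/20/10% and OR 3:
- control cumulative proportions: 0.10, 0.30, 0.70, 0.90
- control odds: 0.111, 0.429, 2.333, 9
- odds divided by 3: 0.037, 0.143, 0.778, 3
- treated cumulative proportions: 0.036, 0.125, 0.4375, 0.75

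**Simulated power, two arms, 3,000 trials per setting (%).**

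| Control distribution | OR | Chi-square, full table | Rank-sum | t-test on scores |
|---|---|---|---|---|
| 5 grades, centred (10/20/40/20/10) | 2 | 16.7 | 31.5 | 32.0 |
| | 3 | 40.2 | 64.4 | 64.8 |
| | 4 | 60.6 | 83.5 | 82.7 |
| 5 grades, high (3/7/20/40/30) | 2 | 15.3 | 30.4 | 29.2 |
| | 3 | 37.2 | 59.3 | 57.4 |
| | 4 | 56.7 | 79.5 | 76.1 |
| 6 grades, flat | 2 | 17.0 | 33.1 | 33.5 |
| | 3 | 38.3 | 64.5 | 64.9 |
| | 4 | 57.2 | 84.0 | 83.4 |

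The largest gap between rank-sum and full-table chi-square is 84.0 − 57.2 = 26.8 points. The largest between rank-sum and t-test is 79.5 − 76.1 = 3.4 points.

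**Collapsed rate.** Section 2 speaks of comparing rates, so a two-category table is the closer reading of its chi-square. In the centred example at OR 3, the share in the top two grades is 1 − 0.70 = 30% in control and 1 − 0.4375 = 56.25% in the treated arm.
- mean proportion: (0.30 + 0.5625)/2 = 0.43125
- null SE: √(2 × 0.43125 × 0.56875/30) = 0.1279
- alternative SE: √[(0.30 × 0.70 + 0.5625 × 0.4375)/30] = 0.1233
- z = (0.2625 − 1.96 × 0.1279)/0.1233 = 0.096, so power is about 54%

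Against 64.4% for rank-sum the loss is about 10 points. In the high-weighted case at OR 3, cutting at the top grade gives the same two proportions and so the same 54%, against 59.3%: about 5 points.

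**Wider ranges.** With 10,000 trials per setting, 3 to 6 grades and flat, centred or low-weighted distributions:
- full-table chi-square loses 7 to 19 points (3 or 4 grades) or 14 to 29 points (5 or 6 grades) against rank-sum
- chi-square on the split nearest the middle loses 3 to 15 points
- in three arms, full-table chi-square loses 7 to 21 or 14 to 32 points against Kruskal-Wallis
- the t-test and ANOVA on scores stay within 1 point of the rank test

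With two further distributions weighted to high grades, the collapsed chi-square lost 0 to about 3 points and the t-test about 2 to 5.

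**Type I error, two arms.** Full-table chi-square 3.8% to 5.5%, collapsed chi-square 4.7% to 5.5%, rank-sum 4.8% to 5.3%, t-test 4.8% to 5.4%. None is inflated materially.

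**The case for a change.** The strongest case for a change is that the gap can be shown without assuming ordered grades: a reader cannot tell which route applies to these items. The authors gave scales for Fugl-Meyer and peak torque, so they could have done so here. The remedy would be wording only, and a fixed assignment would stop the test from being chosen after the results are known. Chi-square can also do worse than the collapsed range suggests if the cut is far from the middle. In the centred example at OR 3, the top grade alone is 10% against 25%. The null SE is √(2 × 0.175 × 0.825/30) = 0.0981 and the alternative SE √[(0.09 + 0.1875)/30] = 0.0962, so z = (0.15 − 1.96 × 0.0981)/0.0962 = −0.44 and power is about 33%.

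The factual part stands. The gap is in fact wider than the items usually singled out: Section 2 names no outcome at all, and self-care ability and the general motor-function item also lack a scale. What does not follow is that the plan prescribes a poor analysis. Nowhere does it send these items to chi-square. The list ends in the word for scores, and the survey is meant to quantify; both fit the mean-based route better. The larger full-table losses belong to an analysis that Section 2 does not describe. Nor can these items be set aside as secondary, because the documents rank no outcomes.

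**Conclusion.** No change to the plan is needed. This is missing detail, and no stated rule is shown to give a wrong result. If the items are summed or numeric scores, ANOVA and the t-test apply as written. If they are ordered grades coded as scores, the same tests stay within about 1 to 5 points of the power of a rank test, so adding Kruskal-Wallis or rank-sum brings no material gain. A loss that matters arises only if an analyst chooses chi-square for graded items: 3 to 15 points for a rate split near the middle under flat, centred or low-weighted distributions, 0 to 3 under two high-weighted ones, and more for an extreme cut or the full table. Even then validity is unaffected, since type I error stays near 5%.

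These sizes rest on assumed scales, assumed grade distributions and proportional-odds shifts at 30 per arm. The therapist items are not covered, because the number of therapists is not given. A report would ordinarily name the scale and the test used for each item, and that is enough for a reader to judge the result.

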1.2 Method

Both the control group and the two treatment groups received conventional rehabilitation therapy such as exercise therapy (once a day,

40 minutes a time, 5 times a week), occupational therapy (once a day, 30 minutes a time, 5 times a week), low-frequency electricity (once a day, 20 minutes a time, 5 times a week), acupuncture and moxibustion therapy (once a day, 20 minutes a time, 5 times a week), which complied with the recommendations on rehabilitation treatment in the 2017 edition of the Guidelines for Early Rehabilitation Treatment of Stroke in China; Intelligent isokinetic therapy adds isokinetic muscle strength training to the lower limb flexion and extension muscles of hemiplegia in the above treatments. The intelligent portable isokinetic tester of this project team was used for isokinetic training of the affected knee flexor and extensor muscles. The patient's seat backrest was adjusted to 85° , and the waist and shoulder cross straps were fixed. The proximal thighs of the test subjects were fixed with nylon buckles, the lateral condyle of the femur was the axis, and the length of the arm was 12 on the scale. The distal ankle of the lower leg was fixed above the ankle. Before training, passive joint movements were performed on the knee and ankle joints to avoid joint damage, And conduct three low resistance warm-up exercises. Choose $60^{\circ}/s$, $90^{\circ}/s$, and $120^{\circ}/s$ angular velocity isokinetic training based on the patient's specific situation. Train 10 times for each angular velocity, with 15 seconds of rest between each cycle, and 2 minutes of rest between each cycle. Train for 4 cycles according to the patient's tolerance, with an appropriate amount of training to cause

moderate muscle fatigue and no fatigue on the second day (a total of 25 minutes per training session). Train each muscle group once a day, 5 days a week, for a total of 3 weeks. The control group received 110 minutes of daily training, while the observation group received 135 minutes of daily training. Traditional isokinetic therapy has the same treatment parameters as the intelligent isokinetic group in this project group.

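### No primary outcome is named and P < 0.05 applies to each of about five to eight outcomes, so with no true effect the chance of some false group difference is about 10% to 34%, not 5%

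*Combined protocol and SAP*

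**What the plan says.** Section 1.3 opens the clinical assessments with "Evaluate lower limb motor function using the Fugl Meyer method", giving a motor score out of 34 and a balance score out of 14. It continues with "Muscle strength, muscle tone examination, motor function, and self-care ability scores", and adds peak torque at 60 degrees/s, described as "representing the maximum muscle force generated by muscle contraction". The section also remarks that "the peak torque measurement of knee joint flexion and extension is particularly stable", which leaves open whether flexion and extension are analysed separately. Satisfaction questionnaires follow.

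Section 2 specifies that "the inter group comparison is performed using one-way analysis of variance, the pairwise comparison between groups is performed using LSD test", with t-tests and chi-square tests where they apply. The only decision rule is that P < 0.05 "indicates a statistically significant difference".

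Neither section names a primary outcome, an order of testing or an adjustment across outcomes. Section 1.3 speaks highly of peak torque, but as a way to measure strength; it does not make peak torque the endpoint that decides the trial.

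**The concern.** When several outcomes are each tested at 0.05 and none is designated in advance, the plan does not say which result answers the trial's question. Any one significant outcome can be presented as the finding. The 0.05 threshold then limits the error of each test, but not the chance that the trial reports at least one difference that is not there.

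Two conclusions are exposed: that added isokinetic training is better than conventional rehabilitation alone, and that the project team's own device differs from the traditional one. Once results have been seen, no later analysis can restore a pre-specified primary outcome.

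**Working it through.** The plan states no overall error rate, power or sample-size figure, so there is nothing of its own to reproduce.

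**Inputs from the documents**
- Three arms of 30 (Section 1.1), so the F test has 2 and 87 degrees of freedom.
- Level 0.05 per test; one-way ANOVA, then LSD pairs (Section 2).
- Outcomes (Section 1.3). Taken literally there are seven: Fugl-Meyer motor, Fugl-Meyer balance, muscle strength, muscle tone, motor function, self-care and peak torque. There are five if motor function is the Fugl-Meyer motor score and muscle strength is peak torque. There are eight if all seven are separate and torque is split into flexion and extension.

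**Assumptions**
- Outcomes are normal, with the same correlation between every pair. The documents give no correlation, so 0 to 0.9 is shown.
- LSD pairs are read only after a significant F. This favours the plan and holds each single outcome at 5% when there is no true effect.
- Questionnaires are left out.

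**Independent outcomes.** The chance of at least one false result among K outcomes is 1 − 0.95^K:
- K = 5: 1 − 0.95^5 = 0.226
- K = 6: 0.265
- K = 7: 0.302
- K = 8: 1 − 0.95^8 = 0.337

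**Correlated outcomes.** Simulation, 40,000 trials per correlation, no true effect; chance of any false group difference:

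| Outcomes | corr. 0 | 0.3 | 0.5 | 0.7 | 0.9 |
|---|---|---|---|---|---|
| 5 | 22.6% | 20.8% | 18.9% | 15.4% | 10.5% |
| 8 | 33.6% | 30.4% | 26.0% | 19.9% | 12.5% |

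One outcome gives 5.0%. Independent repeat simulations agree to within about 1 percentage point.

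**Which false claims.** Same setting, five to eight outcomes:

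| False claim | corr. 0.7 to 0 | corr. 0.9 | One outcome |
|---|---|---|---|
| Any difference from control | 13% to 29% | 9% to 11% | 4% |
| Training better than control | 7% to 16% | 5% to 6% | 2% |

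**Device against device.** Suppose both devices truly beat control by the same amount (0.5 to 1.2 SD, assumed). A false difference between them then appears in 14% to 34% of trials at correlation 0.7 to 0, and in 9% to 12% at 0.9. With one outcome it is about 5%.

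**If LSD does not wait for a significant F.** One outcome alone gives 12.1% for its three pairs. Five to eight outcomes give 23.2% (five, correlation 0.9) to 64.8% (eight, correlation 0).

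**The case against.** - **The plan promises no 5% error across outcomes.** True: 0.05 is a per-test threshold, so this is missing pre-specification, not a contradiction or a miscalculation. But the rule as written lets each outcome support its own claim, and that is the problem.
- **The count could be lower.** Treating Fugl-Meyer as one score and merging both overlapping pairs leaves four: Fugl-Meyer, tone, self-care and torque. Four outcomes give about 18% to 9.5% (correlation 0 to 0.9), still about two to almost four times 5%.
- **34% is a corner case.** It needs eight separate, uncorrelated outcomes. Most of these measures concern motor function in the same patients, so moderate to high correlation is more plausible. At 0.5 to 0.9 the range is about 10% to 26%. This objection stands as to size; the excess remains.
- **Some outcomes may be categorical.** Section 2 does not say which, so the normal model is an approximation.
- **The condition that LSD follows a significant F is not in Section 2.** Correct. The number of outcomes is then not the only source of inflation, and the main figures understate the problem.
- **Small rehabilitation trials usually report several outcomes, and results may already be known.** No outcome needs to be dropped. The second point changes the remedy but does not remove the need for one.

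**Conclusion.** The concern holds. With five to eight outcomes each tested at 0.05 and none primary, the chance of at least one false group difference is about 10% to 34% when there is no true effect. The low end pairs five outcomes with correlation 0.9; the high end pairs eight with correlation 0. A false device-versus-device difference has a similar chance, about 9% to 34%, when both devices work equally well.

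These figures rest on 30 per arm, normal and equally correlated outcomes, and LSD only after a significant F. The exact size depends on a correlation and an outcome count that the documents do not settle. That the rate exceeds 5% does not: it is about twice 5% even at correlation 0.9.

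**What to change.** In Section 2:
1. Name one primary outcome at the end of treatment ("for a total of 3 weeks"), for example the Fugl-Meyer lower limb motor score or peak torque at 60 degrees/s. The choice is the sponsor's. State whether the end score or the change from baseline is tested.
2. Test it by the overall F at 0.05, and read the LSD pairs only if F is significant. This condition is a second change, since Section 2 does not now contain it. Together the two changes bring the chance of a false group difference on the deciding outcome to 5% when there is no true effect.
3. Label all other outcomes secondary or exploratory and report them as group differences with 95% confidence intervals.
4. Make and date the choice before results are seen.

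Section 1.1 describes recruitment in the past tense ("from January 2022 to January 2023 were selected"), so results may already be known. If they are, label the conclusions exploratory instead of naming a primary outcome now.

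**Cost.** Only wording, if results have not been seen; treatments, visits and sample size do not change. Some secondary results can no longer be called significant at an unadjusted 0.05, and the main claim rests on one test. If both devices beat control equally (assumed effects), the chances are:

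| True effect | F significant | A given device shown better than control | Both shown better |
|---|---|---|---|
| 0.8 SD | 89% | 83% | 77% |
| 0.5 SD | 49% | 40% | 31% |

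The last two columns are the ones to weigh for a claim about a device. If results are known, the cost is weaker, exploratory conclusions.
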